6.8.2.2. Eye Assessment

Eye testing will include distance and near visual acuity (best-corrected or pinhole using the Snellen Chart and Near Reading Card), Humphrey visual field testing (using the 10-2 protocol with a red-on-white target), and ophthalmoscopy.

Only subjects who pass all other inclusion/exclusion criteria at screening should be sent for these eye examinations. Results from subsequent eye tests during the study will be compared with the screening results to track any changes in subjects' vision.

For each method of eye assessment, change from baseline (Yes/No) and change from baseline clinically significant (Yes/No) will be listed, and if there are sufficient changes they will be summarized by treatment group and compared with Fisher's exact test.

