## 2. Schedule of Activities

## Study Schedule Protocol I9F-MC-SCAA: Part A, Periods 1 through 3

Study Day	Screen	Periods 1 to 3								FDC a	ED	Notes
		-28 to -2	-1	1 b	2	3	4	5	6			
Admit to CRU		X										
Discharge from CRU					X							
Physical examination	X	X								X	X	
Ethanol and urine drug screens	X											An additional ethanol and urine drug screen may be done at the discretion of the investigator at readmission to the CRU.
Ophthalmic examination	X				X					X	X	See Section 9.4.4.2 for details.
12-Lead ECG (hours)	X		0, 1, 2, 4, 6, 8, 12	24	48				X	X	X	ECGs coinciding with PK sample time points are to be conducted as close as possible to PK sampling. See Section 9.4.3 for other details.
Vital signs (hours)	X		0, 1, 2, 4, 6, 8, 12	24	X	X	X	X	X	X	X	See Section 9.4.2 for details.
Clinical laboratory values (hours)	X	X			48				X	X	X	Screening tests will occur at local laboratories and other analyses will be at central laboratory. Blood will be collected on Day -1 for both local and central labs. Investigator will review local lab results before dosing in each period.
LY3323795 study drug			X									Subjects are required to fast before and after drug administration. See Section 6.3.1 for details.
LY3323795 plasma PK samples (hours)			0, 0.5, 1, 2, 3, 4, 6, 8, 12	24	48	72	96	120	144			A maximum of 5 additional plasma samples per subject may be drawn during the study at the discretion of the investigator or sponsor. These additional samples may be drawn to measure LY3323795 or A $\beta$ concentrations.
PD plasma samples (hours)			0, 0.5, 1, 2, 3, 4, 6, 8, 12	24	48	72	96	120	144			A maximum of 5 additional plasma samples per subject may be drawn during the study at the discretion of the investigator or sponsor.

Study Day	Screen	Periods 1 to 3								FDC a	ED	Notes
	-28 to -2	-1	1 b	2	3	4	5	6	7			
Storage plasma samples (hours)			0, 0.5, 1, 2, 3, 4, 6, 8, 12	24	48	72	96	120	144			This is not an additional draw; sample will be taken from PD blood sample and stored separately. Stored samples will be used for other assays yet to be determined.
Weight/height	X	X								X	X	Height measured at screening only.
Urine collection (hours)			0-24	24-48								Urine to be collected continuously during the 2 separate collection periods (0-24 and 24-48 hours).

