**Figure SCAA.1. Illustration of study design for Protocol I9F-MC-SCAA.**

### **5.1.1. Part A: Dose-Escalation Study**

Part A is a dose-escalation study that will be conducted in 2 alternating cohorts (Cohorts 1 and 2), each consisting of approximately 9 subjects (6:3 subjects, LY3323795:placebo at each dose level) who will participate in 3 study periods (total of 6 dose levels in the 2 cohorts). The number of subjects intended to be enrolled is detailed in Section 5.2. The first 4 dose levels of LY3323795 are anticipated to be 0.3 mg, 1 mg, 3 mg, and 10 mg. Doses 5 and 6 are anticipated to be 30 and 100 mg, but will be confirmed following PK data reviews. See Section 5.1.1.1 for details of dose-escalation decisions.

Sentinel dosing will be used in this study. For all dose levels, LY3323795 and placebo will be administered first to a sentinel group of 2 subjects (1:1, LY3323795:placebo). These subjects will be followed for 24 hours postdose; if the dose is well tolerated, dosing of the remaining 7 subjects in the cohort may begin.

The proposed dose levels may be adjusted based on emerging safety and PK data (see Section 7.4.1).

Subjects will be admitted to the CRU on Day -1 (see Part A Schedule of Activities, Section 2) and will remain as inpatients for at least 48 hours after dosing on Day 1, after which they may be discharged at the discretion of the investigator. Subjects will then return for outpatient visits for up to 144 hours postdose (Day 7). The washout time between doses for a given subject will be at least 14 days.

PK and PD (plasma A $\beta$ ) data, as well as safety assessments, including clinical laboratory tests, ECGs, AEs, vital signs, ophthalmic examinations, and neurological surveys, will be collected at various time points pre- and postdosing with LY3323795/placebo, as described in Part A Schedule of Activities (Section 2). However, exact time points for PK/PD and safety assessments may be modified based on interim PK/PD results (see Section 5.1.1.1).

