## 5.4. Scientific Rationale for Study Design

This study will be conducted to determine the safety and tolerability of LY3323795 in healthy subjects.

The crossover design in Part A of this study will allow each subject to act as their own control and allow for an assessment of within- and between-subject variability in evaluating tolerability and PK of different doses of LY3323795. The placebo-controlled, dose-escalation strategy allows safety and PK/PD data to be obtained with a large degree of within-subject control data.

The collection times for PK samples and washout period between doses are based on the predicted PK and PD of LY3323795 from nonclinical studies. Based on the estimated half-life of approximately 23 hours, sample collection for up to 144 hours should be sufficient to fully assess the concentration-time profile, and a washout period of at least 14 days should be sufficient to ensure that there is no carryover between periods. Either or both may be revised based on reviews of preliminary PK data generated during the study.

It is intended that a range of 3 doses of LY3323795 be administered in Part B of the study based on the LY3323795 exposures and plasma PD response observed in Part A. The aim is to determine a dose level that produces a substantial reduction in CSF A $\beta$ . The exact doses of LY3323795 administered in Part B will be determined after reviewing the emerging data from Part A, as well as available data from any previous doses carried out in Part B. However, doses in Part B will not exceed a dose that has been assessed in Part A as being safe and well tolerated.

To minimize confounding effects of the catheterization on A $\beta$  concentrations, the indwelling catheter for CSF collection will be inserted approximately 4 hours prior to study drug administration to allow A $\beta$  CSF measurements to stabilize. Previous CSF catheter studies have shown large variability in CSF A $\beta$  in the first few hours of collection after catheterization (Ereshefsky et al. 2007).

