Statistical Analysis Plan: I9F-MC-SCAA

Single-Ascending Dose Study to Assess the Safety, Tolerability, Pharmacokinetics, and Pharmacodynamics of LY3323795 in Healthy Subjects

NCT02989389

Approval Date: 20-Dec-2016

**1. Statistical Analysis Plan:
I9F-MC-SCAA: Single Ascending Dose Study to Assess
the Safety, Tolerability, Pharmacokinetics, and
Pharmacodynamics of LY3323795 in Healthy Subjects**

Confidential Information

The information contained in this Statistical Analysis Plan (SAP) is confidential and the information contained within it may not be reproduced or, otherwise, disseminated without the approval of Eli Lilly and Company or its subsidiaries. This document and its associated attachments or appendices are subject to United States Freedom of Information Act (FOIA) Exemption 4.

LY3323795

A Phase 1 study of LY3323795 in healthy subjects that will be conducted in 3 parts. Parts A and B are subject- and investigator-blind, placebo-controlled, randomized studies. Part A is a single ascending dose, 3-period, 2-cohort, crossover study to assess the safety, tolerability, and plasma pharmacokinetics (PK) and pharmacodynamics (PD) of LY3323795 in healthy volunteers. Part B is a single-dose, 3-cohort study to assess the safety, tolerability, and the plasma and cerebrospinal fluid (CSF) PK and PD of LY3323795. Part C is an open label, 2-period, fixed-sequence study in healthy volunteers to evaluate a potential cytochrome P450 (CYP) 3A4 interaction when LY3323795 is coadministered with itraconazole.

Eli Lilly and Company
Indianapolis, Indiana USA 46285

Phase 1 Statistical Analysis Plan electronically signed and approved by Lilly on date provided below.

Approval Date: 20-Dec-2016 GMT

2. Table of Contents

| Section | Page |
|--|------|
| 1. Statistical Analysis Plan: I9F-MC-SCAA: Single Ascending Dose Study to Assess the Safety, Tolerability, Pharmacokinetics, and Pharmacodynamics of LY3323795 | 1 |
| 2. Table of Contents..... | 2 |
| 3. Revision History..... | 4 |
| 4. Objectives..... | 5 |
| 4.1. Primary Objective | 5 |
| 4.2. Secondary Objectives..... | 5 |
| 4.3. Exploratory Objectives..... | 5 |
| 5. Summary of Study Design | 6 |
| 5.1. Determination of Sample Size..... | 6 |
| 5.2. Method of Assignment to Treatment | 7 |
| 6. A Priori Statistical Methods | 8 |
| 6.1. General Considerations | 8 |
| 6.2. Multicenter Studies | 8 |
| 6.3. Multiple Comparisons/Multiplicity..... | 8 |
| 6.4. Patient Disposition | 8 |

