6.8.2. Statistical Evaluation of Safety

The safety analyses will be conducted for Part A, B, and C separately. The safety and tolerability of treatment will be assessed by summarizing the following:

- Adverse Events
 - Treatment-emergent adverse events (TEAEs) by:
 - System Organ Class (SOC) and Preferred Term (PT)
 - Maximum severity
 - Considered to be related to investigational produce by investigator
 - Serious Adverse Events (SAEs)
 - Adverse events (AEs) leading to discontinuation
- Vital signs and weight
- Laboratory measurements
- Electrocardiograms (ECGs)
- Eye assessments

Safety parameters will be listed and summarized using standard descriptive statistics, where appropriate. Additional analysis will be performed, if warranted, upon review of the data.

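### Fisher's exact test on eye changes needs each subject counted once, which fails for pooled Part A periods and for Part C; a lasting change is also recounted in later periods

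*SAP*

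**What the plan says.** For each eye assessment method, SAP 6.8.2.2 lists change from baseline and clinically significant change from baseline as yes/no. It adds that "if there are sufficient changes they will be summarized by treatment group and compared with" Fisher's exact test. Protocol 10.3.1.2 has the same rule. Neither defines the treatment groups, names the counting unit (subject or subject-period), or treats any part differently.

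The baseline is a single one: "Results from subsequent eye tests during the study will be compared with the screening results". In the Part A schedule (protocol section 2), the row "Ophthalmic examination" has entries at screening, on Day 3 of each period, at final discharge and at early discontinuation. There is no predose examination in any period.

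On design, the SAP's opening summary states "Part A is a single ascending dose, 3-period, 2-cohort, crossover study", and protocol 5.4 states "The crossover design in Part A of this study will allow each subject to act as their own control". Protocol 5.1.1 gives three periods per subject, an allocation of "6:3 subjects, LY3323795:placebo at each dose level", and "The washout time between doses for a given subject will be at least 14 days". Part C (protocol 5.1.3) gives the same 8 subjects LY3323795 (LY below) alone and then with itraconazole.

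SAP 6.8.2 adds "The safety analyses will be conducted for Part A, B, and C separately". That separates the parts but says nothing about periods within a part.

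**The concern.** Fisher's exact test assumes that every record is an independent subject belonging to one group. One rule is written for three designs, and only Part B is parallel-group with one record per subject. Applied to Part A periods combined by treatment, or to Part C, it breaks that assumption.

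The second issue does not depend on the test. With screening as the only reference, an examination in Period 2 or 3 cannot distinguish a new change from one already present. A change first seen after LY that outlasts the washout is scored again under whatever comes next. If that is placebo, the placebo column gains a change that placebo did not cause. If it is a higher dose, that dose looks worse than it was. In Part C the sequence is fixed, so any such recount falls on the itraconazole period. What is at stake is the accuracy of the eye-safety table and of any p-value attached to it.

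**Working it through.** The plan states no rate, power or sample size for this comparison, so there is no figure to reproduce. The record counts below come from the documents; rates, persistence and sequences are assumptions.

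**1. Records in Part A.** 2 cohorts × 3 periods × 6 = 36 LY records, and 2 × 3 × 3 = 18 placebo records: 54 records from 18 subjects. If each subject has placebo once, all 18 are in both groups.

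**2. Within one dose level.** The 6 LY and 3 placebo subjects are different people. With no drug effect and a lasting 10% background per period, the Period 3 test rejects in under 4% of 20,000 simulated trials at the nominal 10%, under each of the three allocations in step 3. Independence holds, but power is low: 5/6 vs 0/3 gives p = 0.048 and 4/6 vs 0/3 gives p = 0.167.

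**3. Pooled, 36 vs 18.** Under the same null, rejection at nominal 10% over 20,000 simulated trials was:

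| Assumed allocation | Rejection |
|---|---|
| One placebo period per subject | 0.2% |
| Independent 6:3 draw each period | 6.1% |
| Same 3 per cohort always on placebo | 22.4% |

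With independent examinations at 10% the rate is about 4.5% under all three. The spread therefore comes from repeated subjects, and its direction depends on sequences that are not stated.

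**4. Recounting, small example.** One subject per cohort has a lasting change on LY in Period 1, placebo in Period 2 and LY in Period 3. Counted at first observation: 2/36 vs 0/18. Counted against screening: 2 × 2 = 4 of 36 on LY (11%) and 2 of 18 on placebo (11%), p = 1.00. With one subject per dose level, the eye stopping rule is not met.

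**5. Recounting, expected rate.** Let q be the chance of a lasting change per LY dose, with none from placebo. If each subject has one placebo period, equally often in Periods 1, 2 and 3, the share of placebo records flagged is [0 + q + (1 − (1 − q)²)]/3:

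- q = 5%: (0.05 + 0.0975)/3 = 4.9%
- q = 10%: (0.10 + 0.19)/3 = 9.7%
- q = 20%: (0.20 + 0.36)/3 = 18.7%

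With an independent draw each period, q is replaced by 2q/3, giving 3.3%, 6.5% and 12.7%. If the same subjects always take placebo, the share is 0.

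**6. Effect of the stopping rule.** Protocol 7.4.1 stops dosing at the level and further escalation when at least 2 subjects at one dose level have a related ophthalmic finding. Suppose every new LY change is judged related and data end at the stopping dose. At q = 20%, only about 15% of simulated trials reach Dose 6. The flagged placebo share under one placebo period per subject falls from 18.7% to about 5% of all placebo records (about 3% as an average of per-trial rates). At q = 10% it falls from 9.7% to about 5.6%. If changes were judged unrelated, the rule would bite less.

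**7. Part C.** There are 8 subjects and two treatments, so an 8-versus-8 table holds each subject twice. Fisher's test does not apply.

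**The case against.** The strongest reply is that nothing in the documents says periods will be pooled. The 6:3 allocation is set per dose level in protocol 5.1.1 and 5.2 and SAP 5.2, so dose-level groups are a natural reading, and on that reading subjects do not overlap. This stands: the independence problem in Part A is conditional. It does not remove recounting within a dose level, and it does not help Part C.

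Second, little rests on the test. It runs only if changes are sufficient, SAP 6.1 plans no formal hypothesis testing, every change is listed, and investigator and sponsor review eye tests before each escalation (protocol 5.1.1.1). This also stands and limits the severity, although none of it corrects the table.

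Third, recounting needs a change that persists at least 14 days after a single dose of a drug with a projected half-life of about 23 hours (protocol 5.4). The documents give no rate for that. Fair: every q above is an assumption.

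A reader might go further and infer that the planned test inflates false positives, citing the 22%. The documents do not support that. It needs both pooling, which is not stated, and the same subjects on placebo throughout, which fits poorly with subjects acting as their own control. Under the other two allocations the rejection rate stays below the nominal 10%.

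**Conclusion.** The concern holds in a limited form, as a minor point. As written, the rule permits Fisher's exact test on repeated subjects in pooled Part A data, and directs it to Part C if changes are sufficient; it is not valid in either. It is acceptable in Part B and, as regards independence, within a Part A dose level. Recounting of lasting changes follows from the screening baseline and the schedule. It affects the descriptive table as well as any test, and within-dose comparisons as well as pooled ones.

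The size cannot be stated from the documents. The illustrations rest on assumed rates, complete persistence and assumed sequences. A reader might take the 18.7% placebo figure as what to expect, but it ignores the eye stopping rule; with all changes judged related, the same assumptions give about 3 to 5%. Nor do the documents support a claim that escalation or any other decision would be misled, since none uses this p-value.

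**What to change.** In SAP 6.8.2.2, with matching wording in protocol 10.3.1.2:

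1. Use Fisher's exact test only where each subject contributes one record: Part B, or LY versus concurrent placebo within a single Part A dose level. Report pooled Part A and all Part C eye changes descriptively, and name the unit and the groups of each table.
2. Keep the comparison with screening. Add a by-period summary that separates changes new or worse since the previous examination from those already present, attributed to the treatment at first observation.

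No permutation or other replacement test is needed. The cost is SAP wording and minor programming, with no new examinations. One limit remains: on the current schedule, a change that persists and one that recurs in consecutive LY periods cannot be told apart.

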6.8.2.3. Laboratory Tests

The listing of patients with abnormal high or low laboratory values, based on Covance reference ranges, at any time postbaseline will be created.

The listing of patients with elevations in hepatic laboratory tests as defined below will be created.

- An alanine aminotransferase (ALT) or aspartate aminotransferase (AST) measurement greater than or equal to 3 times (3×) the Covance upper limit of normal (ULN) during the treatment period.
- A total bilirubin measurement greater than or equal to 2 times (2×) ULN during the treatment period.

6.8.2.4. Vital Signs and Weight

Plot of vital signs and weight over time will be created for each patient.

6.8.2.5. Electrocardiogram Intervals and Heart Rate

Analysis of corrected QT (QTc) data from ECG monitoring in a Phase 1 trial is performed to judge the extent and/or risk of QT prolongation. A scatter plot will be generated to explore the relationship between QTc and drug exposure, and will assess the mean change in QTc using

Fridericia's formula as a function of plasma drug concentration. The QTc analysis will not include ECGs collected in Part C (itraconazole interaction), due to the potential for non-LY3323795-induced changes in QTc. Frequency tables of QTc changes from baseline and large QTc values may also be obtained in accordance with International Conference on Harmonisation (ICH) guidance, and additional analyses may be conducted if required.

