**Statistical Analysis:**

The sample size for Part A is customary for Phase 1 studies evaluating safety, PK, and/or PD parameters, and is not based on statistical mean estimation. Parts B and C are not formally powered to detect a prespecified anticipated effect; however, precision intervals have been calculated to show what may be observed for changes in cerebrospinal fluid (CSF) A $\beta$  and effect of itraconazole on LY3323795 given the sample sizes.

No formal interim analyses are planned for this study. Interim access to data (IAD) is scheduled to occur throughout the study. The purpose of these IAD reviews is to examine the safety and or PK/PD data and guide dose selections.

All investigational product and protocol procedure adverse events will be listed, and if the frequency of events allows, safety data will be summarized using descriptive methodology. Safety laboratory parameters, vital signs, and electrocardiogram parameters will be listed and summarized using standard descriptive statistics for values at each time point as well as changes from baseline.

PK parameter estimates for LY3323795 will be calculated using standard noncompartmental methods of analysis. The primary parameters for analysis will be Cmax and AUC of LY3323795. Other noncompartmental parameters, such as half-life, apparent clearance, and apparent volume of distribution may be reported.

For Parts A and B, plasma concentrations of A $\beta$ 1-40 and A $\beta$ 1-42 will be summarized for each dose group based on the nadir concentration (Cnadir) and the time to reach Cnadir (tnadir).

In Part B, CSF concentrations of A $\beta$ 1-40, A $\beta$ 1-42, and CCI will be summarized for each dose group based on the Cnadir, tnadir, and the 24-hour average values, expressed as a percentage change from baseline. Statistical analysis of CSF A $\beta$ 1-40 and A $\beta$ 1-42 concentrations obtained over the fixed-scheduled sampling period will be analyzed using a repeated-measures analysis with the primary statistical estimation of the overall mean percentage change from baseline and 90% confidence interval among the LY3323795 doses and placebo at each post dose time point.

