- Dose-dependent QT corrected for heart rate (QTc) prolongation occurred following repeated administration in dogs of doses at and above 5 mg/kg; peak changes at 5 mg/kg and 120 mg/kg were +7 msec and +31 msec, respectively. No qualitative electrocardiogram (ECG) abnormalities were observed. Decreases in heart rate also occurred following repeated administration in dogs of doses at and above 5 mg/kg; peak changes at 5 mg/kg and 120 mg/kg were -15 bpm and -39 bpm, respectively.
- In a single-dose cardiovascular safety study in dogs, QTc prolongation was noted at doses of 5 mg/kg ( $\leq +4$  msec) and 30 mg/kg ( $\leq +9$  msec). At all dose levels, minor decreases in heart rate were observed; at the 30-mg/kg dose level, a 6-bpm reduction in heart rate was observed (maximally). Also at the 30-mg/kg dose, minimally decreased systolic pressure (-7 mmHg), mean arterial pressure (-5 mmHg), and  $dP/dt_{max}$  (-240 mmHg/sec) occurred during the first 6 hours postdose.
- In rats, minimal increases in autofluorescent granules in the retinal pigmented epithelium were noted at the 150-mg/kg dose level and were considered nonadverse.
- The no-observed-adverse-effect level (NOAEL) of LY3323795 was 120 mg/kg in dogs and 150 mg/kg in rats.

Itraconazole, an antifungal agent, will be administered in Part C of this study as it is known to be a potent inhibitor of CYP3A, and is commonly used in drug interaction evaluations. Peak plasma concentrations of itraconazole are reached within 2 to 5 hours following oral administration. As a consequence of nonlinear PK, itraconazole accumulates in plasma during multiple dosing. Bioavailability is increased when itraconazole is administered with food. The terminal half-life of itraconazole generally ranges from 16 to 28 hours after single dose and increases to 34 to 42 hours with repeated dosing. Once treatment is stopped, itraconazole plasma concentrations decrease to an almost undetectable concentration within 7 to 14 days, depending on the dose and duration of treatment. The primary metabolite of itraconazole is hydroxy-itraconazole. Additional information including possible side effects of itraconazole can be found in the product insert.

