#### **10.3.1.2. Statistical Evaluation of Safety**

Safety parameters that will be assessed include safety laboratory parameters, CNS monitoring, eye assessments, vital signs, and ECG parameters. The parameters will be listed and summarized using standard descriptive statistics. Additional analyses will be performed if warranted upon review of the data. The statistical analysis plan will contain all details on the evaluation of safety measurements.

Analysis of QTc data from ECG monitoring in a Phase 1 trial is performed to judge the extent and/or risk of QT prolongation. A scatter plot will be generated to explore the relationship between QTc and drug exposure, and will assess the mean change in QTc using Fridericia's formula as a function of plasma drug concentration. The QTc analysis will not include ECGs collected in Part C (itraconazole interaction), due to the potential for non-LY3323795-induced changes in QTc.

Frequency tables of QTc changes from baseline and large QTc values may also be obtained in accordance with International Conference on Harmonisation guidance, and additional analyses may be conducted if required.

For each method of eye assessment, change from baseline (yes/no) and change from baseline clinically significant (yes/no) will be listed, and if there are sufficient changes they will be summarized by treatment group and compared with Fisher's exact test.

Additional analyses may be performed for the purpose of fulfilling the Clinical Trial Registry requirements.

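### The only exposure-QTc analysis the plan commits to is an exploratory scatter plot; a prespecified placebo- and time-adjusted mixed model would give an estimate with usable uncertainty from data already collected

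*SAP*

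**What the plan says.** SAP 6.8.2.5 gives the purpose of the QTc analysis: it "is performed to judge the extent and/or risk of QT prolongation". The method is that "A scatter plot will be generated to explore the relationship between QTc and drug exposure", and the plot "will assess the mean change in QTc using" Fridericia's formula, as a function of plasma concentration. ECGs from Part C are excluded. The rest of the section is optional: "Frequency tables of QTc changes from baseline and large QTc values may also be obtained", and "additional analyses may be conducted if required".

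Protocol 10.3.1.2 has the same text and passes the detail on: "The statistical analysis plan will contain all details on the evaluation of safety measurements". On QTc the SAP adds nothing to the protocol wording.

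Three other provisions bear on the point:
- The protocol synopsis says that "electrocardiogram parameters will be listed and summarized using standard descriptive statistics for values at each time point as well as changes from baseline". SAP 6.8.2 also lists ECGs among the safety summaries.
- Protocol 7.4.1 has a stopping rule based on individual QTc readings, compared with the same period's predose mean.
- Protocol 9.5.1 says that samples from placebo subjects are not planned to be assayed.

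**The concern.** QTc is a named nonclinical signal. Protocol 3.2 reports that "Dose-dependent QT corrected for heart rate (QTc) prolongation occurred following repeated administration in dogs", with peak changes of +7 msec at 5 mg/kg and +31 msec at 120 mg/kg. Table SCAA.2 puts the dog QTc LOEL Cmax at about 5 times the Cmax projected for 100 mg. The study's data are meant to help design and dose later trials.

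Judging the extent of an effect needs an estimate and its uncertainty. A scatter plot supplies neither, and three features make a line drawn through it by eye or by simple regression hard to trust:
- **Clustering.** Each subject contributes many points over several periods.
- **Time of day.** After a morning dose, concentration rises and falls over hours in which QTc may also vary with the clock.
- **Placebo.** Placebo subjects have no assayed concentration, and no rule sets it to zero. The concurrent control can therefore drop out of the exposure-QTc reading.

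Elsewhere the SAP is more explicit. The Part C PK model (6.9.2) has a random subject effect and a 90% CI, and the Part B CSF model (6.10.2) is a repeated-measures analysis.

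**Working it through.** **Plan's own figure.** Neither document states a QTc SD, margin, power or interval, so there is nothing to reproduce for the analysis itself. The related multiple in Table SCAA.2 does reproduce: 1018 / 210 = 4.85, stated as 5.

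**Data available from Part A** (Protocol 5.1.1, Schedule of Activities, 9.4.3).
- Post-dose ECG times paired with PK: 1, 2, 4, 6, 8, 12, 24 and 48 h and Day 7, which is 9 per period.
- Active subject-periods: 6 dose levels x 6 = 36. Placebo subject-periods: 6 x 3 = 18.
- Active pairs: 36 x 9 = 324. Placebo ECG time points: 18 x 9 = 162. All come from 18 subjects if everyone completes.
- Baseline: 3 sets of triplicates before dosing in each period.

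**Effect of clustering alone.** Design effect = 1 + (m - 1) x ICC, with m = 9 per subject-period and the ICC assumed.

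| Assumed ICC | Design effect | Naive SE / true SE = 1/√(design effect) |
|---|---|---|
| 0.2 | 1 + 8 x 0.2 = 2.6 | 62% |
| 0.4 | 1 + 8 x 0.4 = 4.2 | 49% |
| 0.6 | 1 + 8 x 0.6 = 5.8 | 42% |

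These ratios apply to a contrast between subject-periods. They show the order of the problem rather than the exact SE of a slope.

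**Simulation of Part A** (1,500 trials per setting). From the documents: 18 subjects, 3 periods, 9 post-dose pairs, 23 h half-life, and the AUC and Cmax projected for 100 mg. Assumed: one placebo period per subject, subject and subject-period SDs of 3 or 5 msec each, residual SD 6 msec, a true effect of 10 msec at the top-dose Cmax, and a time-of-day change of 0 or up to 6 msec either way. The top dose is 100 mg or, as a second scenario, 42 mg, where the projected AUC meets the exposure cap (3,450 / 8,180 x 100 = 42.2).

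The table shows how often a one-sided 95% upper bound falls below the true effect (nominal 5%).

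| Analysis | No time effect | Time-of-day fall | Time-of-day rise |
|---|---|---|---|
| Simple line, active data only | 18% to 23% | 41% to 55% | 2% to 10% |
| Simple line, placebo added at 0, time and clustering ignored | 16% to 20% | 25% to 28% | 5% to 15% |
| Treatment, time, concentration, subject and period terms | 5% to 6.4% | 4.5% to 5.5% | 4.8% to 5.5% |

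For the active-only line, bias was about -1.8 to -1.9 msec under the fall and +1.6 to +2.0 msec under the rise. For the adjusted model it was within about 0.2 msec throughout.

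Two-sided coverage follows from the same runs by normal approximation. With no bias, coverage = 2Φ(1.645 x mean SE / empirical SD) - 1. For the 100 mg case with SDs of 3 msec this is 2Φ(1.645 x 1.21 / 2.24) - 1 = 2Φ(0.889) - 1 = 63%. With SDs of 5 msec it is 2Φ(1.645 x 1.52 / 3.23) - 1 = 2Φ(0.774) - 1 = 56% (its bias of 0.11 msec is negligible).

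**Second simulation, on the slope.** With other assumed SDs and a time-of-day shift of 7 msec, a simple line's 90% CI covered the true slope in 45% to 67% of runs. Its prediction at Cmax was off by about 4.5 to 5 msec in either direction. The adjusted model covered 88% to 91% with negligible bias.

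**Sensitivity to what the SDs describe.** If subject and period SDs (4 and 5 msec) belong to raw QTc, subtracting the period baseline removes them and leaves shared baseline error. Simple-line coverage with no time effect was then 72%, against 57% if they belong to the change itself.

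**The case against.** The strongest reply is that the plan never promises what is said to be missing. It uses the plot to explore a relationship and plans no line, SE, interval or threshold from it. SAP 6.1 says there is no formal hypothesis testing, and Part A is not sized on estimation. The coverage figures therefore grade an analysis that is not in the SAP. This stands: the plan is under-specified, not in contradiction with itself.

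A reader might also infer that QT risk rests on the plot alone, or that the points are wholly uncorrected. The documents do not support either. The plotted variable is change in QTcF, so baseline is already subtracted. ECG parameters are summarized by time point and as change from baseline, and placebo subjects on the same schedule at every dose level allow an informal time-matched look. The stopping rule covers individual readings. None of these, however, gives a concentration-response estimate with its uncertainty.

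It is tempting, too, to say that the plot would hide a QT effect. The direction of error is unknown. An assumed time-of-day fall makes a simple line too reassuring; a rise makes it overpredict, and its upper bound can even become conservative.

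Finally, all SDs, time-of-day sizes and the 10 msec effect are assumptions. One placebo period per subject is compatible with 6:3 over three periods but is not stated. The adjusted model was tested only with variance components taken as known, so its performance with estimated components in 18 subjects may be somewhat worse.

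**Conclusion.** The point holds as a gap in prespecification. The SAP sets out to judge the extent or risk of QT prolongation, is named by the protocol as the place for all safety-analysis detail, and commits on exposure-QTc only to an exploratory plot. No planned output gives a placebo- and time-corrected change in QTcF with a valid interval.

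Anyone who reads a slope from the plot will overlook that 324 active pairs come from 18 subjects, as well as any time-of-day pattern. Under the assumptions shown, a nominal 90% interval would cover roughly 45% to 70%, and the prediction at Cmax could be off by about 2 to 5 msec either way if QTc shifts by 6 to 7 msec over the day. The clustering part does not depend on a time-of-day effect; the bias part does. The numbers are illustrative and are not forecasts for this trial.

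The stronger statement, that the plan sets out to bound the QT effect and fails, goes too far because no bound is promised. This is a worthwhile, inexpensive improvement to a secondary part of the safety analysis. It is not a flaw in the design or in subject-level QT monitoring.

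**What to change.** Keep the scatter plot in SAP 6.8.2.5 as a diagnostic and add a prespecified analysis for Part A:
- **Response:** change in QTcF from the same period's predose mean.
- **Fixed effects:** treatment (LY3323795 or placebo), nominal time, centred baseline, and concentration, set to 0 for placebo.
- **Random effects:** subject and subject-by-period.
- **Report:** placebo-corrected change in QTcF with a 2-sided 90% CI at each dose's geometric mean Cmax. This matches the 2-sided 0.10 level in SAP 6.1.
- **Part B:** its few single ECGs are not excluded by the present text and differ from Part A's triplicates. Show them separately, or only on the plot.
- **Part C:** excluded, as now.

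The cost is SAP wording and some programming, with no new data or visits. The downside is reliance on a linear concentration-QTc relation, for which the retained plot serves as the check. Fixing the model before unblinded data are seen also avoids choosing it afterwards.
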